8.7 DEMOGRAPHICS, MEDICAL HISTORY, BASELINE CHARACTERISTICS, AND CONCOMITANT MEDICATIONS

Demographic data and other baseline characteristics, medical history, and concomitant medications will be summarized by means of descriptive statistics. Where applicable, comparisons among treatment groups will be performed using an analysis of variance (ANOVA) model for continuous variables and a Cochran-Mantel-Haenszel (CMH) test for categorical variables

8.8 EFFICACY ANALYSES

8.8.1 Primary Efficacy Endpoint

The primary efficacy endpoint is the proportion of responders for the last 2 weeks of the Treatment Period (responder = a child who experiences >3 SBMs per week for each of the last two weeks of the treatment period) compared to placebo and across treatment groups.

8.8.1.1 Analysis of the Primary Efficacy Endpoint

The weekly SBM rate for each patient will be computed, as described in **Section 8.4.1**, for each week of the 8-week treatment period. The change from baseline in mean weekly SBM rate will be analyzed using a linear mixed-effects model with fixed effects for gender (stratification

variable), treatment, week, and the corresponding baseline value; a random intercept for patient will also be specified. The least squares (LS) mean change from baseline will be presented, by treatment group, and the difference in LS means for each plecanatide treatment group compared to placebo will be presented, with 95% confidence intervals and corresponding statistical *p*-values.

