Statistical Methods	
Analysis Populations
 
Analysis populations include the Safety population, the Intent-to-treat (ITT) population, and the Per-Protocol (PP) population. The Safety population will include all patients who were randomly assigned to a treatment group and received at least 1 dose of study drug. The ITT population will include all patients who were randomized to receive study drug. The PP population will be used for sensitivity analyses, and will consist of all patients in the ITT population without any significant protocol violations. The ITT population will be the primary population for efficacy analyses.
 
Patient Characteristics and Disposition
 
Demographic characteristics (including age, gender, race, weight, height, and body mass index) and characteristics of patients' CIC history will be summarized by descriptive statistics for each treatment group.
 
Efficacy Analyses
 
Primary Efficacy Analysis
 
The primary efficacy endpoint is the proportion of responders for the last 2 weeks of the Treatment Period (responder = a child who experiences >3 SBMs per week for each of the last two weeks of the treatment period) compared to placebo and across treatment groups. The change from baseline in mean weekly SBM rate will be analyzed using a linear mixed-effects model with fixed effects for gender (stratification variable), treatment, week, and the corresponding baseline value; a random intercept for patient will also be specified. The least squares (LS) mean change from baseline will be presented, by treatment group, and the difference in LS means for each plecanatide treatment group compared to placebo will be presented, with 95% confidence intervals and corresponding statistical p-values.
 
Secondary Efficacy Analysis
 
The secondary efficacy endpoints are:
 
• Change from baseline in weekly average stool consistency (BSFS) score over the 8-week treatment period, and by study week• Change from baseline in the weekly rate of SBMs, by study week• Change from baseline in the weekly rate of CSBMs over the 8-week treatment period, and by study week 
The mean in each period and the change from baseline will be summarized in each treatment group. Differences between treatment groups will be analyzed with an analysis of covariance, including fixed effects for gender (stratification variable) and treatment and corresponding baseline value as a covariate. A least squares mean with 95% confidence intervals will be presented for the difference between each plecanatide group and placebo.
 
Pharmacokinetic Analyses
 
Plasma plecanatide (and its major metabolite SP-338) concentrations will be assessed for all patients pre-dose on Day 1, and at Week 4 and Week 8 visits.

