2.4.1 Efficacy Endpoints

2.4.1.1 Primary Efficacy Endpoint

The primary efficacy endpoint is the proportion of responders for the last 2 weeks of the Treatment Period (responder = a child who experiences >3 SBMs per week for each of the last two weeks of the treatment period) compared to placebo and across treatment groups.

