2.4.1.2 Secondary Efficacy Endpoints

The secondary efficacy endpoints are:

- Change from baseline in weekly average stool consistency (BSFS) score over the 8-week treatment period, and by study week
- Change from baseline in the weekly rate of SBMs, by study week
- Change from baseline in the weekly rate of CSBMs over the 8-week treatment period, and by study week

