8 STATISTICAL METHODS

The objectives of the study are to assess the safety and efficacy of plecanatide 0.5, 1.0, and 1.5 mg dosed daily, compared with placebo.

Before database lock and un-blinding, a formal statistical analysis plan (SAP) will be written and will include details of all statistical methods to be used to analyze the efficacy and safety data. The SAP will supersede the protocol with respect to the analyses specified, although the primary analysis described in this section will remain unchanged.

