8.2 SAMPLE SIZE AND POWER CONSIDERATIONS

Based on data from two phase 3 trials conducted by the sponsor in adults with CIC, assume a mean change from baseline in weekly SBM rate for placebo-treated subjects of 1.2 with a standard deviation of 2.6; similarly, for plecanatide-treated subjects, assume a mean change from baseline of 3.1 with a standard deviation of 4.0. Then, a *t*-test for the difference in means of two independent samples with unequal variances, at a two-sided level of significance of 0.05 and 80% power to detect the assumed difference in means, would require 51 subjects per treatment group. Since study SP304202-13 is being conducted in adolescents with CIC, and the primary analysis of the primary endpoint will be an ANCOVA using a linear mixed-effects model, the sponsor believes that 30 subjects per treatment group (placebo and 3 dose levels of plecanatide), yielding a planned target enrollment of a total of 120 subjects, will prove sufficient for achieving the primary objective of this phase 2 study.

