8.4 GENERAL CONSIDERATIONS

Categorical variables will be summarized by the number and percentage of patients in each category level. Continuous variables will be summarized by number of observations, mean, standard deviation (SD), median, minimum, and maximum values. Where data are collected over time, both the observed data and change from Baseline will be summarized at each time point.

Summaries will be presented by treatment group (placebo, and plecanatide 0.5 mg, 1.0 mg, and 1.5 mg), and combined active doses. All data collected in the eCRF will be presented in listings.

All statistical tests will be two-sided at the 5% level of significance, unless stated otherwise.

No interim analyses are planned.

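### The primary endpoint is a Weeks 7–8 responder proportion, but the specified primary analysis is a mixed model of change in weekly SBM rate, and no test of the responder proportion is planned.

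*Combined protocol and SAP*

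**What the plan says.** **Endpoint.** Section 2.4.1.1 states: "The primary efficacy endpoint is the proportion of responders for the last 2 weeks of the Treatment Period". Section 8.8.1 repeats this with the definition "responder = a child who experiences >3 SBMs per week for each of the last two weeks of the treatment period", and says the proportion is to be compared with placebo and across groups. Both endpoint passages in the Synopsis agree. By the diary windows in Section 8.4.2, the last two weeks are Week 7 (Days 43–49) and Week 8 (Days 50–56).

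**Analysis.** Section 8.8.1.1 computes a weekly SBM rate for each of the 8 treatment weeks, then states: "The change from baseline in mean weekly SBM rate will be analyzed using a linear mixed-effects model with fixed effects for gender". The other terms are treatment, week, baseline and a random patient intercept; there is no treatment-by-week term. The output is LS mean differences from placebo with 95% CIs and p-values. The Synopsis places the same model directly after the responder definition. Section 8.2 confirms that this is intended: "the primary analysis of the primary endpoint will be an ANCOVA using a linear mixed-effects model".

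**Status of SBM change.** It appears only among the secondary endpoints, in Section 2.4.1.2 as "Change from baseline in the weekly rate of SBMs, by study week" and in the Synopsis.

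**Room for the SAP.** Section 8 lets a later SAP supersede the protocol's analyses, "although the primary analysis described in this section will remain unchanged".

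**The concern.** The endpoint and its analysis differ in two ways. The endpoint is binary and the analysis continuous. The endpoint covers Weeks 7–8; the model, lacking a treatment-by-week term, gives one treatment effect across Weeks 1–8. The analysis text never mentions a responder or a proportion.

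If the plan is followed literally, the primary p-values and CIs describe a quantity the protocol does not call primary, while the named primary endpoint has no planned test, difference or interval. Once the data are unblinded, either result could be presented as the answer to the primary objective. The two can differ: one patient can gain many SBMs on average without exceeding 3 in both final weeks, and another can pass the threshold with a modest gain.

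**Working it through.** **1. Is the responder proportion tested anywhere?** Each candidate in the text:

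| Section | What it provides | Covers the primary responder proportion? |
|---|---|---|
| 8.8.1.1, Synopsis | Mixed model of change in weekly SBM rate | No |
| 8.8.2.2 | By-week mixed model, giving Week 7 and Week 8 mean differences | No: means, and secondary |
| 8.8.4.1 | Gender-stratified CMH, rate differences, CIs | No: four exploratory endpoints, defined as at least 3 and a gain of at least 1, in 4/8 or 6/8 weeks |
| 8.7 | CMH for categorical variables | No: baseline-type data |
| 8.4 | "Categorical variables will be summarized by the number and percentage of patients in each category level" | Count and percentage only |
| 8.4.1 | Rule of at least 4 compliant diary days per week | No: exploratory responder analyses only |

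The most the named endpoint receives is a count and percentage by arm.

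**2. Window.** The endpoint uses 2 of 8 weeks and the model uses all 8, so 6/8 = 75% of the modelled weeks lie outside the window.

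**3. The plan's own sample size.** Inputs from Section 8.2: mean change 1.2 (SD 2.6) on placebo and 3.1 (SD 4.0) on plecanatide, two-sided 0.05, 80% power, unequal-variance t-test.

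- Difference = 3.1 − 1.2 = 1.9; sum of variances = 6.76 + 16.00 = 22.76.
- n = 51: SE = √(22.76/51) = 0.668; noncentrality 1.9/0.668 = 2.84; power 80.3%. At n = 50, power is 79.5%. The stated 51 per group is reproduced.
- n = 30: SE = √(22.76/30) = 0.871; noncentrality 2.18; power 57.1%.

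Both figures concern mean change. Nothing in Section 8.2 sizes the responder endpoint.

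**4. How much the choice matters (assumption-based).** The documents give no responder rates, so a model is needed. Assumptions: each patient has a gamma-distributed SBM rate, constant over 8 weeks; weekly counts are Poisson; arm means are baseline + 1.2 and baseline + 3.1; the 8.2 SDs of change serve as SDs of counts; mean baseline is 0.75, 1.0 or 1.5 SBMs/week; 30 per arm; no dropout. With SDs read as single-week values, the between-patient variance is SD² − mean; read as 8-week averages, it is SD² − mean/8. A response is more than 3 SBMs in both Week 7 and Week 8. A Welch t-test on 8-week means stands in for the mixed model.

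| Reading of the 8.2 SDs | Placebo rate | Active rate | Responder power (chi-square) | t-test power | n per arm for 80% responder power |
|---|---|---|---|---|---|
| Single week | 12–17% | 30–39% | 43–46% | 68–74% | 67–75 |
| 8-week average | 13–19% | 30–38% | 37% | 57–60% | 87–89 |

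The last column uses n = [1.96√(2p̄(1−p̄)) + 0.84√(p₀(1−p₀)+p₁(1−p₁))]²/(p₁−p₀)². For example, 17.4% against 39.0% gives p̄ = 0.282 and (1.247 + 0.520)²/0.216² ≈ 67. In this model the two tests disagreed on significance in 29–34% of simulated trials, mostly with only the mean test significant (26–32%).

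**5. Check without the count model.** For a plain 20-point gain at 30 per arm (pooled normal approximation), power is 49% (10% vs 30%), 39% (20% vs 40%), 35% (30% vs 50%) and 34% (40% vs 60%), with 62, 82, 93 and 97 per arm needed for 80%.

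**The case against.** The study is declared exploratory, makes no multiplicity adjustment (Section 8.8.6) and ties no stated decision rule to the primary p-value. Responder status can be derived from diary data already collected, and Section 8.4.1 already scores missing days as 0 SBMs. Section 8.8.1 does name a comparison with placebo, so arguably only its method is missing, and the SAP is meant to hold the details of all methods. This lowers the consequence but does not remove the contradiction. The exploratory label does not say which result answers the primary objective. Section 8.2 identifies the mixed model as the primary analysis and Section 8 fixes the primary analysis, so the likelier reading is that a responder test added in the SAP would not be primary. That is an inference, and no separate SAP was available.

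The criticism of the simulation has more force. The baseline range comes from nowhere in the documents, and holding each patient's rate constant is a strong assumption. Splitting the single-week variance equally between patient and week lowers the responder rates to roughly 6–12% and 22–33%, although responder power stays at about 44–47%. The rates and the disagreement figure are therefore illustrative. The power shortfall is steadier, and the finding does not depend on either.

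**Conclusion.** The concern holds and must be fixed before unblinding. The plan names a Weeks 7–8 responder proportion as primary and assigns it an analysis of a different variable over a different window, consistently in Section 8.8.1.1, the Synopsis and Section 8.2. This is text that is wrong as written, not merely a missing detail, and the conclusion rests on the wording alone. Three figures need no outside assumption: 6 of 8 modelled weeks lie outside the endpoint's window, the 51 per group in Section 8.2 is for mean change, and 30 per group gives 57% power on those same inputs. That the responder comparison at 30 per arm would have about 37–46% power, and need 67–89 per arm for 80%, rests on the count model described above.

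**What to change.** Choose one route and amend the protocol before unblinding.

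**(a) Keep the responder endpoint.** In Section 8.8.1.1 and the Synopsis, make the primary analysis a comparison of Weeks 7–8 responders, each dose against placebo, with the difference and 95% CI. The gender-stratified CMH of Section 8.8.4.1 is a ready choice, though not the only acceptable one. State one diary rule: either missing days count as 0 SBMs, or at least 4 compliant days are required in each of the two weeks. Patients with no data are non-responders under both. Keep the mixed model of 8-week SBM change as a named secondary analysis, and rewrite Section 8.2 on a responder basis. Cost: an amendment, a new sizing argument, and acceptance of lower power at 30 per arm (about 37–46% on the assumptions above).

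**(b) Keep the analysis.** Rename the primary endpoint as change from baseline in weekly SBM rate over the 8-week treatment period, in both Synopsis passages and in Sections 2.4.1.1 and 8.8.1. Add the Weeks 7–8 responder proportion as a secondary endpoint with the CMH test and a stated diary rule, and limit the Synopsis's secondary SBM endpoint to the by-week form. The sentence in Section 8.2 on the primary analysis then agrees with the endpoint. Cost: the four wording changes, matching edits to the secondary lists (Synopsis, 2.4.1.2, 8.8.2), and one extra analysis by a method already in the protocol.

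Neither route needs new data.

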	
BMs, rescue medication use for constipation, abdominal pain, and other symptoms. At Weeks 1, 4, and 8 of the Treatment Period, patients will return to the clinic to undergo safety and efficacy assessments.
 
Posttreatment Follow-up Period: For 2 weeks after the last dose of study drug, patients will continue to complete their daily electronic diaries. Patients will then return to the clinic for a final Follow-up visit at the end of Week 10.
 
The planned duration of participation in this study will be approximately 14 weeks from signing of informed consent/assent through posttreatment.

Study Drug	Plecanatide 0.5, 1.0, or 1.5 mg tablets and matching placebo for oral administration
Treatment	
Following a 28-day Screening Baseline Period, patients will be randomly assigned to 1 of 3 plecanatide doses (0.5, 1.0, or 1.5 mg) or to matching placebo. Study drug will be provided as a 4-week supply of tablets in blister packs. It will be distributed on Day 1 and replenished at Week 4. Patients will take the assigned dose of study drug each morning approximately at the same time for 8 weeks.
 
Dulcolax® will be provided as a rescue laxative that can be used if a patient has not had a bowel movement for at least 72 hours. Patients will be advised that it is preferred that they NOT take rescue medication for the period from 24 hours before to 72 hours after Day 1 of dosing.

Number of Patients and Population	Approximately 120 adolescents with CIC will be randomized (~30 in each treatment group) into the study. Eligibility for study enrollment (2 or fewer SBMs per week, adequate diary entry compliance and proper use of rescue medication) will be confirmed by electronic diary entries made during each week of the two-week baseline diary assessment.
Key Inclusion Criteria	Male or female adolescents 12 to less than 18 years of age diagnosed with CIC based on the Rome III criteria for child/adolescent functional constipation.
Key Exclusion Criteria (abbreviated)	
Medical history or conditions that may be affecting GI motility or defecationLack of willingness to use Dulcolax® as the only laxative.Non-compliance with eDiary and rescue medication use.

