8.4.1 Missing Data Conventions

In general, data will not be imputed for safety analyses.

The weekly SBM (CSBM) rate is the sum of the SBMs (CSBMs) recorded for the days in the week for which a BM response is recorded in the daily diary. Note that this is equivalent to a “worst case” analysis in that the SBM (CSBM) rate for the week is the sum of the SBMs (CSBMs) recorded for the days in the week for which BMs were reported, plus 0 SBMs (0 CSBMs) for each day in the week for which the BM response is missing. In any week in which no BM response is recorded, the weekly SBM (CSBM) rate will be set to 0 in any summary or linear mixed-effects model analysis involving the weekly SBM (CSBM) rate. In particular, for a randomized patient who withdraws from study participation prior to the end of the study, the patient is considered to have a weekly SBM (CSBM) rate equal to 0 for any weeks remaining in the planned duration of the study for which the patient has no BM responses recorded.

The weekly average CIC-related abdominal pain score is the average of the non-missing, abdominal pain scores recorded in that week, i.e., the weekly average is the sum of the abdominal pain scores recorded in the diary in the given week, divided by the number of pain scores recorded in the week. In any week in which a patient has no diary days for which an abdominal pain score is recorded, the weekly average abdominal pain score will be set to missing. In any linear mixed-effects model analysis involving the weekly average abdominal pain score, if the average score is set to missing in a given week, it will be left as missing in the linear model. In particular, for a randomized patient who withdraws from study participation prior to the end of the study, the weekly average abdominal pain score will be set to missing for any weeks remaining in the planned duration of the study for which the patient has no abdominal pain data.

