8.4.3 Baseline Definition

For each safety parameter, the most recent valid assessment recorded before randomization will be used as the baseline for all analyses of that safety parameter.

For efficacy parameters, the baseline values will be derived from data collected in the 2-week electronic diary assessment at the end of the Screening Period (baseline). The last 14 days of diary entries prior to Day 1 will be the default standard for derivation of these values.

The baseline SBM (CSBM) weekly rate will be the weekly average number of SBMs (CSBMs) recorded during the 2-week baseline assessment period. Baseline stool consistency, severity of straining during a BM, and abdominal symptoms will be calculated as follows: for each week of the baseline assessment, the weekly average is the sum of the non-missing scores recorded during the week divided by the total number of non-missing scores recorded during that week; the baseline is then equal to one-half of the sum of the two weekly average scores..

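### The trial is sized with unequal SDs (2.6 placebo, 4.0 plecanatide), but the 8.8.1.1 mixed model by default pools one variance over all four arms; if those SDs hold, dose-versus-placebo standard errors are about 10% too large

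*Combined protocol and SAP*

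**What the plan says.** - **Section 8.2 (sample size).** The planning values for change from baseline in weekly SBM rate are a mean "for placebo-treated subjects of 1.2 with a standard deviation of 2.6" and, "for plecanatide-treated subjects, assume a mean change from baseline of 3.1 with a standard deviation of 4.0". The test is a t-test for the "difference in means of two independent samples with unequal variances", and 80% power at two-sided 0.05 "would require 51 subjects per treatment group". The section then plans 30 per group, citing the adolescent population and the mixed-model ANCOVA.
- **Section 8.8.1.1 (primary analysis).** Fixed effects are gender, treatment, week and baseline, and "a random intercept for patient will also be specified". The only contrasts reported are each dose against placebo, with 95% intervals and p-values. No group-specific variance, robust standard error or degrees-of-freedom method is named.
- **Section 8.4.1 (missing data).** "In any week in which no BM response is recorded, the weekly SBM (CSBM) rate will be set to 0", including weeks after withdrawal.
- **Section 8 (opening).** Detail of the methods is left to an SAP written before database lock and unblinding. The SAP may supersede the protocol on analyses, except that the primary analysis stays as described.

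**The concern.** The plan expects the active arms to vary more than placebo, and uses that expectation to size the trial. The analysis model then, on its usual reading, ignores it. Equal allocation makes a pooled variance harmless in a two-arm comparison. It does not do so here, because the pooled variance comes from one placebo arm and three active arms and is weighted three to one towards the larger SD. The contrasts affected are the only ones the model reports.

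What is at stake is precision. Intervals would be wider than the data justify, and some power would be lost in a trial that already enrols fewer patients than its own calculation asks for. Section 8.2 also gives the mixed-model ANCOVA as part of the reason why 30 per group will do. On the 8.2 SDs, the common-variance form of that model has less power than the t-test used for sizing.

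**Working it through.** **Inputs.** From 8.2: means 1.2 and 3.1 (difference 1.9), SDs 2.6 and 4.0, two-sided 0.05, 51 per group calculated, 30 planned. Assumptions: the 8.2 SDs describe the patient-level change and hold in each dose, with 30 patients in each of four arms. If the SDs describe single weeks, the ratios are unchanged provided the between- and within-patient parts scale alike.

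**1. The plan's own figure.** Unequal-variance t-test power (noncentral t) is 79.5% at 50 per group and 80.3% at 51. The stated 51 reproduces. At 30 per group the same test has 57.1% power.

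**2. Why the model reduces to patient means.** Empty SBM weeks become 0, so every randomized patient has eight weekly values. With complete, balanced weeks, the treatment contrast from a random-intercept model is a comparison of patient means using one variance pooled over four arms.

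**3. Standard errors at 30 per arm.**
- Pooled variance = (2.6² + 3 × 4.0²)/4 = (6.76 + 48)/4 = 13.69; model SE = √(2 × 13.69/30) = 0.955.
- True SE = √((6.76 + 16)/30) = 0.871.
- Ratio 1.097, so 9.7% too large.
- For comparison, pooling only the two arms being compared gives (6.76 + 16)/2 = 11.38 and √(2 × 11.38/30) = 0.871. The excess comes entirely from the other two active arms.

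**4. Interval width.** Pooled: t(116 df) × SE = 1.981 × 0.955 = 1.892. Arm-specific: t(49.8 df) × SE = 2.009 × 0.871 = 1.750. Ratio 1.081. The excess is smaller than for the SE because the arm-specific interval uses a larger t quantile.

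**5. Error and power.**
- Null error with the pooled SE: 2 × [1 − Φ(1.892/0.871)] = 3.0%. Simulation gave 3.0 to 3.3%.
- Power with the pooled SE: Φ((1.9 − 1.892)/0.871) = 50.4%, against 57.1% with arm-specific variances.
- At 51 per arm: 75.2% against 80.3%.
- The fall from 80% to 57% (about 23 points) is due to enrolling 30 and not 51. Pooling adds about 7 points.

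**6. Does the baseline covariate rescue it?** The Synopsis requires "Eligibility for study enrollment (2 or fewer SBMs per week" in each baseline week, and "The baseline SBM (CSBM) weekly rate will be the weekly average number of SBMs (CSBMs) recorded during the 2-week baseline assessment period". Baseline therefore lies between 0 and 2, and its SD is at most 1.0. With a slope within ±1 (assumed), it removes at most 1.0 from each arm's variance, leaving 5.76 and 15. The SEs become √(2 × 12.69/30) = 0.920 and √(20.76/30) = 0.832, a ratio of 1.106. Power is about 53% against 60%. The gap remains.

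**7. Sensitivity to the active SD** (placebo 2.6, all doses alike; 3.0 and 3.5 are assumed values):

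| Active SD | Pooled SE | True SE | Excess | Power, pooled vs arm-specific |
|---|---|---|---|---|
| 4.0 | 0.955 | 0.871 | 9.7% | 50% vs 57% |
| 3.5 | 0.852 | 0.796 | 7.0% | 60% vs 64% |
| 3.0 | 0.750 | 0.725 | 3.5% | 71% vs 73% |
| 2.6 | equal | equal | none | see fix |

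**8. Withdrawal** (assumed 10, 20 or 30% at a random week, later weeks set to 0, simulated with the 8.2 SDs): SE excess 9 to 11%; power 47, 45 and 43% against 54, 52 and 49%.

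**The case against.** **The text is silent; it does not pool expressly.** A reader might infer that the protocol prescribes a common variance. It does not: a random intercept is compatible with arm-specific variances. The finding rests on the default form of the model, and should be read that way.

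**The SAP can settle it.** A reader might take the clause in section 8 that keeps the primary analysis unchanged to mean that only a protocol amendment will do. That reading is too strong. Naming the variance structure of the same model is a detail, and section 8 assigns detail to the SAP.

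**Pooling is conventional.** Sizing with unequal SDs does not oblige the sponsor to model them. That is fair, but it does not change the arithmetic: on the plan's own inputs the reported intervals would be too wide.

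**The SDs may not carry over.** They come from adult phase 3 trials, which section 2.1.4 describes as testing 3 and 6 mg. The documents give no SDs for 0.5 to 1.5 mg or for adolescents. This stands, and the size of the effect depends on it.

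**False positives.** A reader might infer that the mismatch inflates type I error. On the 8.2 SDs it does the opposite. Error above 5% needs SDs that differ between doses. For example, with one dose at 4.0 and the other arms at 2.6, error for that dose is about 8%, but nothing in the documents supports that pattern. The 3% figure also needs a null in which the drug changes the spread and not the mean. If the drug is inert, the SDs are equal and pooling is correct.

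**The remedy has its own weakness.** Weekly counts bounded at 0 are likely to be skewed. With assumed gamma data and the 8.2 SDs, arm-specific null error is about 5.5 to 6%, against about 3.3 to 3.7% pooled. The power gain, about 8 points, persists.

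**Conclusion.** The inconsistency is real and modest. If the 8.2 SDs hold in all three doses, at 30 per arm and with the model in its default form, dose-versus-placebo standard errors are about 10% too large, 95% intervals about 8% too wide, null error about 3%, and derived power about 50% where 57% was available. The documents state no power at 30 per arm; these figures follow from the 8.2 inputs.

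It would be wrong to blame the model for the whole shortfall from 80%, since most of it comes from the sample size. No size is claimed here for the by-week SBM, CSBM or stool-consistency models.

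Sections 2.4.1.1 and 8.8.1 define the primary endpoint as a responder proportion. If a responder analysis becomes primary, this model is supportive and the point matters less.

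**What to change.** State in 8.8.1.1, or in the SAP before unblinding:

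> *Random-intercept and residual variances will be estimated separately by treatment group, with Satterthwaite degrees of freedom. If this model does not converge, patient means over the eight weeks will be analysed by a Welch-type method with arm-specific variances.*

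The SAP alone is enough if a responder analysis becomes primary.

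One fallback should be named in full; a general reference to robust standard errors would leave the correction open. The one proposed stays close to the model. In 300 simulated trials fitted directly by REML with arm-specific variances, every fit converged and matched the arm-specific analysis of patient means.

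**Cost.** One or two sentences, with no change to data or sample size.
- If SDs are in fact equal, intervals widen by about 1% (t quantile 2.002 on 58 df against 1.981 on 116) and power falls by about 0.6 points (79.7% to 79.1% at SD 2.6; 44.8% to 44.2% at SD 4.0).
- With normal data, simulated null error for the arm-specific form was 4.5 to 5.3%. With strongly skewed data and unequal SDs it may reach about 5.5 to 6%, and the SAP should acknowledge this.
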